10. STUDY CALENDAR

Baseline evaluations are to be conducted within 2-week prior to start of protocol therapy with the exception of scans and x-rays. Scans and x-rays must be done \leq 4 weeks prior to the start of therapy.

Assessments must be performed prior to administration of any study agent. Study assessments and agents should be administered within \pm 3 days of the protocol-specified date, unless otherwise noted.

Procedure	Pre-Study	Cycle 1			Cycles 2+	End of Txt Visit	30 Day F-U Encounter ³	2-6 Month F-U
	Baseline ¹	Day 1 ^{2,b}	Day 8 ⁴	Day 15 ⁵	Day 1 ²			
Dabrafenib and Trametinib ^A		DT ----- DT						
INCB039110 ^B		I-----I						
Informed Consent ^a	X							
Demographic	X							
Medical History	X	X	X	X	X			
Concurrent Medication	X	X	X	X	X			
Serum pregnancy test (B-Hcg)	X ^c	X ^c						
Physical Examination	X	X		X	X	X		
Vital Signs (BP ^d , HR, body temperature)	X ^d	X ^d	X ^d	X ^d	X ^d	X ^d		
ECOG Performance Status	X	X	X	X	X	X		
Dermatology Examination ^e	X				X			X ^e
Height	X							
Weight	X	X			X	X		
Ophthalmology Examination ^f	X				X			
12 Lead EKG	X	X			X			
Hematology/Clinical Chemistry ^g	X	X	X	X	X ^h	X		
Coagulation ⁱ	X							
Tumor Measurements ^j	X ^j				X ^j			
PK Analysis ^k					X ^k			
Optional Tumor Biopsies ^l	X ^l		X ^l			X ^l		
Blood BRAF testing ^m		X		X	X	X		
Rash Prophylaxis ⁿ		X ⁿ		X ⁿ	X ⁿ			
AE assessment ^o	X	X	X	X	X	X	X	
Long term Follow up ^p								X ^p

Color Photography ^q	X ^q				X ^q			
Loperamide ^r	X ^r							

- A. Dabrafenib and Trametinib: doses as assigned; Dabrafenib BID and Trametinib QD.
- B. INCB039110: dosing as assigned per dose level.
- 1. All Pre-study assessments must be completed within 14 days prior to first dose, except for Scans that must be done within 28 days prior to first dose.
- 2. Assessment throughout the study is calendar based starting from first day of dosing (Day 1) in the first cycle of treatment. Dose interruptions should not alter the assessment schedule for any subsequent treatment cycle. Assessment for each visit can be done within 3 days of the projected visit date.
- 3. Follow up encounter, which can be carried out over the phone, should be 30 days from last dose of study drugs (\pm 3 days).
- 4. Medical History, Concurrent Medications, Vital Signs, ECOG Status, Hematology and Blood Chemistry panels will be completed prior to Day 8 treatment.
- 5. Physical Exam, Medical History, Concurrent Medications, Vital Signs, ECOG Status, Hematology and Blood Chemistry panels will be completed prior to Day 15 treatment.
 - a. Informed Consent can be obtained within 28 days prior to the first dose.
 - b. If within 3 days of screening, this assessment does not need to be repeated on Day 1 of the first dose
 - c. Serum Pregnancy test (Woman of childbearing potential only) if done within 72 hours of first dose does not need to be repeated on Day 1 of the first dose.
 - d. In patients with blood pressure of systolic >140 mmHg and/or diastolic >90 mmHg, a second reading should be taken at least 1 minute later, with the two readings averaged to obtain a final BP measurement.
 - e. Dermatological Examination done at screening and then every 8 weeks (2 cycles). For patients enrolling in the expansion cohort who may have been on DT prior to enrolling and have had a recent skin exam, skin exams within 28 days of C1D1 will suffice for eligibility. Skin exams should continue every 2-3 months for 6 months after discontinuation of dabrafenib or initiation of another anti-neoplastic therapy.
 - f. Ophthalmological examination is done at screening, week 4, and annually. For patients enrolling in the expansion cohort who may have been on DT prior to enrolling and have had a recent ophthalmological exam that includes all requirements listed in Section 6.1.14, eye exams within 28 days of C1D1 will suffice for eligibility. Additional ophthalmic exams will be performed only as symptomatically warranted. For further details on requirements of exam see Section 6.1.14.
 - g. Clinical chemistries include sodium, potassium, carbon dioxide/bicarbonate, BUN creatinine, glucose, calcium, magnesium, phosphorus, AST, ALT, total Bilirubin, Alkaline phosphatase, total protein and albumin, LDH. Hematology includes CBC with differentials and platelets. Hematology samples will be collected before study treatment administration and at all applicable study visits
 - h. During Cycle 2, patients will have day 15 (+/- 3 days) clinical chemistries collected as outlined in footnote g above. After cycle 2, clinical chemistries are collected on Day 15 at the investigator's discretion.
 - i. Includes PT, PT-INR, PTT, repeated as indicated. These chemistries may be collected at a remote facility and the results can be faxed to the research team.
 - j. Tumor measurements and radiological exam done every 8 weeks within 7 days of day 1 treatment. Documentation (radiologic) must be provided for patients removed from the study for progressive disease. Brain CT/MRI is required at baseline for patients with melanoma.
 - k. PK samples will be collected pre-dose on Day 1 of Cycles 2, 4 and 6. Also, per Section 6.1.14, for events of visual changes regardless of severity but for which an ophthalmic examination is conducted, a blood sample for PK analysis is encouraged when feasible, and the blood sample should be drawn as close as possible to the time of the event. Also, see section 6.1.16 for PK collection in the setting of Liver Chemistry Changes.
 - l. Optional tumor biopsies will be performed pretreatment. Pre-treatment tissue obtained by biopsy or resection performed according to standard of care may be utilized, provided tissue was obtained within 8 weeks of study entry, and subsequent to the last systemic anticancer therapy received. Optional tumor biopsies will also be performed one week (+/- 3 days) after commencing therapy with the combination as part of the phase I dose escalation and dose expansion cohorts; however, biopsies may be taken at any time, including at the time of clinically meaningful events such as response, disease progression or adverse events of interest. Post-treatment biopsies (following completion of all study therapy) will be optional.

- m. Blood BRAF analysis performed pretreatment C1D1, C1D15, at the beginning of each subsequent cycle and at disease progression (Section 9.1.1).
- n. See table 6.3 for detailed prophylaxis recommended for the first 6 weeks of treatment.
- o. AE assessment starting from the day 1 of dosing throughout the study
- p. After 30 day follow up visit, patient is followed for survival for 2 years. See section 5.6 for full details.
- q. In the case of skin lesions, documentation by color photography, including a ruler to estimate the size of the lesion, is recommended. See section 11.1.3 for full details.
- r. Loperamide should be made available prior to start of study treatment so loperamide administration can begin at the first signs of diarrhea. See table 6-9 for full details.

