5.6 Duration of Follow Up

Participants will be followed for 2 years after removal from study treatment or until death, whichever occurs first. Participants removed from study treatment for unacceptable adverse events will be followed until resolution or stabilization of the adverse event. All patients will have a follow-up encounter 30 days (+ 3 days) after last study treatment for assessment of adverse effects. This encounter can be carried out in clinic or over the telephone. Following discontinuation of dabrafenib, monitoring for non-cutaneous secondary/recurrent malignancies should continue for up to 6 months or until initiation of another anti-neoplastic therapy. Dermatologic skin assessments should be completed every 3 months for 6 months after discontinuation of dabrafenib or initiation of another anti-neoplastic therapy. Participants' vital status will be followed every 6 months (telephone contact is adequate) following removal from the study treatment. Date and cause of death should be provided for participants who become deceased within the 2-year interval following removal from the study treatment.

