7.2 Expedited Adverse Event Reporting

Investigators **must** report to the Overall PI any serious adverse event (SAE) that occurs after the initial dose of study treatment, during treatment, or within 30 days of the last dose of treatment on the local institutional SAE form.

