7.5 Expedited Reporting to the company Supplying Drug (Incyte)

Incyte needs to be notified within 24 hrs of learning of an event. Incyte also needs to be provided a completed SAE form via email. SAE reporting for each subject begins the day the informed consent is signed by the patient and within 30 days after subject has completed or discontinued from the study or has taken last dose of the study drug, or as described in the IST protocol.

SAEs, occurring using Incyte Study drug, are reported in accordance with the effective protocol. SAEs occurring with any another commercial drug are reported to manufacturer of that drug in accordance with regulations and protocol.

Initial Serious Adverse events (SAEs) and/or subsequent follow-up reports should be reported via email to: ***[contact]***. SAE reports should be for a single subject with any additional documents (i.e. discharge summary, relevant test results) included for the same subject as individual attachments to the email. One email can have multiple attachments as long as each attachment contains relevant information for the same subject.

Please email your SAE form with a cover sheet and any additional attachments to the IST email address: ***[contact]***.

Tellex C3i is the PhV Clinical Research Organization (CRO) for Incyte. They will be contacting you for SAE follow-up requests and data clarifications by sending you a data clarification form (DCF). See follow-up section for details on this process. The following is general contact information for Tellex C3i.

TELERX C3I (Incyte PhV CRO)
US SAE [contact]

Tellex C3i tracks any critical outstanding follow-up items and questions and contacts the investigational site via a faxed DCF for the additional requested information until all outstanding queries are resolved. This includes requests for hospital discharge summaries, autopsy reports, and death certificates (if applicable), results of relevant laboratory, and diagnostic tests. The

investigational site faxes the additional information to Telerx C3i, using the Telerx C3i SAE fax number. The site personnel will update all relevant data on the appropriate SAE Report Form or equivalent to include any new or changed information. The Incyte Safety Representative (IC SR) will monitor outstanding queries and take appropriate action needed for resolution.

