<small>Tests performed during pregnancy:</small>  None  Unknown			
 CVS Results:  Normal  Abnormal		 Amniocentesis Results:  Normal  Abnormal	
 Ultrasound Results:  Normal  Abnormal			
Pregnancy Outcome			
<small>Was pregnancy interrupted?</small>  Yes  No <small>If yes, specify:</small>  Elective Termination  Spontaneous Abortion  Ectopic			
<small>Date of Termination:</small> _____			
<small>If pregnancy was not terminated, specify pregnancy outcome (and provide infant outcome information)</small>			
 Vaginal Birth:  Premature		<small>OR</small>  C-Section:  Scheduled  Term  Emergency	
<small>Date of Delivery:</small> _____			
<small>Infant outcome information:</small>  Normal  Abnormal			
<small>Additional Case Details (if needed):</small>			
<small>NOTE: For an initial reporting fax both the Pregnancy Report CRF and Additional Pregnancy Information Fax Page. For follow-up reporting, fax only the Additional Pregnancy Information Fax Page.</small>			

APPENDIX E**CONCOMITANT MEDICATIONS AND NON-DRUG THERAPIES****1.1. Permitted Medications and Non-Drug Therapies**

The investigator must be informed as soon as possible about any medication taken from the time of screening until 30 days after the last dose of study treatment. Any concomitant medication(s), including dietary supplements, taken during the study will be recorded in the eCRF. The minimum requirement is that drug name, dose, and the dates of administration are to be recorded. Additionally, a complete list of all prior surgical procedures will be recorded in the eCRF.

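### Section 5.6 allows the 30-day adverse event contact on Days 30-33 after the last dose, but the study calendar allows Days 27-33, so the last scheduled assessment can come before the 30-day SAE window ends

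*Combined protocol and SAP*

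**What the plan says.** Section 5.6 (Duration of Follow Up) states: "All patients will have a follow-up encounter 30 days (+ 3 days) after last study treatment for assessment of adverse effects". The tolerance is on the late side only. The section allows the contact in clinic or by telephone.

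Study Calendar (Section 10) footnote 3 describes the same contact: "Follow up encounter, which can be carried out over the phone, should be 30 days from last dose of study drugs". It attaches a tolerance on both sides: "should be 30 days from last dose of study drugs (\pm 3 days" (the symbol is plus-or-minus). This matches the calendar's general rule: "Study assessments and agents should be administered within \pm 3 days of the protocol-specified date, unless otherwise noted".

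Two sections set the SAE reporting window that this contact serves. Section 7.2 requires reports to the Overall PI of events during treatment "or within 30 days of the last dose of treatment". Section 7.5 sets the window for reports to the drug supplier: "within 30 days after subject has completed or discontinued from the study or has taken last dose of the study drug".

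In the calendar's adverse event row, the last mark is at the 30-day encounter and the 2-6 month column has none. Footnote p then places the patient in survival follow-up for 2 years.

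**The concern.** Two current passages give different windows for one contact, and a site cannot follow both across the whole range. The general calendar rule does not settle it. That rule yields where something else is noted, and Section 5.6 does note something else, but footnote 3 repeats the two-sided tolerance for this very contact.

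The early side of the calendar window is what matters. The contact exists to assess adverse effects after treatment, and the SAE window runs to Day 30. A contact on Day 27 asks about 27 days. An SAE on the remaining days reaches the data only if the patient, the family or another hospital tells the site. Sites that call early and sites that call on or after Day 30 would then differ in how completely late non-fatal SAEs are found, and Section 13.3.2 lists and tabulates those events together. The safety profile is part of the primary objective in Section 1.1, so a free improvement in completeness is worth having.

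**Working it through.** The plan gives no figure to reproduce. The check is day arithmetic, counting the day of the last dose as Day 0.

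**Inputs**
- Contact under Section 5.6: 30 days, tolerance 0 to +3.
- Contact under calendar footnote 3: 30 days, tolerance -3 to +3.
- SAE window under Sections 7.2 and 7.5, counted from the last dose: through Day 30.
- Last scheduled adverse event assessment in the calendar: this contact.

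**Permitted days**
- Section 5.6: 30 + 0 = Day 30 to 30 + 3 = Day 33.
- Footnote 3: 30 - 3 = Day 27 to 30 + 3 = Day 33.
- Both satisfied: Days 30-33.
- Calendar satisfied but Section 5.6 breached: Days 27, 28 and 29.

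**Part of the SAE window left after the contact** (30 minus the contact day)

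| Contact day | Footnote 3 | Section 5.6 | SAE-window days after the contact |
|---|---|---|---|
| 27 | allowed | not allowed | 30 - 27 = 3 (Days 28, 29, 30) |
| 28 | allowed | not allowed | 30 - 28 = 2 |
| 29 | allowed | not allowed | 30 - 29 = 1 |
| 30-33 | allowed | allowed | 0 |

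The largest gap is 3 of 30 days, 3/30 = 10% of the calendar days in the window. This is a share of days, not of events. The documents give no SAE rate for the post-treatment period and no distribution of contact dates, so no number of missed events can be derived. The most patients who could be exposed is the maximum enrollment of 38 in Section 13.2. That is a ceiling, and the number contacted early could be zero.

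**After the change.** With 0 to +3 in both places, the earliest permitted contact is Day 30 and the largest gap is 30 - 30 = 0 days.

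**The case against.** The strongest reply is that the mismatch has little consequence because other provisions cover the gap. Much of this stands.

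- **Collection does not close at the contact.** A reader might infer from the last mark in the adverse event row that a Day 27 call ends collection. No passage says so. Footnote o has adverse event assessment run for the whole study. The SAE duty to Day 30 does not depend on when the contact takes place. Section 5.6 also follows patients removed for unacceptable adverse events until the event resolves or stabilises. What the documents do support is that no *scheduled* assessment follows the contact.
- **Deaths are not under-counted.** A reader might expect the 30-day death summary in Section 12.2 to suffer. Section 5.6 checks vital status every 6 months and asks for date and cause of any death in the 2 years after treatment. A death on Day 28 would be found with its date, if later.
- **The limit concerns SAEs.** Sections 7.2 and 7.5 set 30 days for serious events. Section 13.3.2 summarises treatment-emergent adverse events without stating a post-treatment window, so a shortfall in all adverse events cannot be claimed.
- **Concomitant medications are a separate matter.** Appendix E, Section 1.1 covers them "until 30 days after the last dose of study treatment", but the calendar marks no medication review at this contact. Moving the contact would not change that.
- **Dose decisions are untouched.** DLTs are counted on days 1-28 of cycle 1 (Section 5.3), and tolerability rests on cycle 1 alone (Section 13.1).
- **The direction of error is not purely downward.** Both passages allow contact up to Day 33, so late contacts could add events from Days 31-33 if the contact date were used as the cut-off.

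The plus sign in Section 5.6 might also be a plus-or-minus sign lost in text conversion. The two-sided symbol survives elsewhere, including in the calendar, so this seems less likely but cannot be excluded. The contradiction would then vanish, while the gap between Day 27 and Day 30 would remain.

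None of these points reconciles the two windows or provides a scheduled question about Days 28-30 after an early call.

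**Conclusion.** The inconsistency is real. Footnote 3 permits contact on three days (27, 28 and 29) that Section 5.6 does not, and a contact on those days puts the last scheduled adverse event assessment 1 to 3 days before the SAE window ends. The effect is limited to how actively non-fatal SAEs on Days 28-30 are sought in patients contacted early.

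This rests on two readings: that Section 5.6 and footnote 3 describe the same contact, which their shared timing and telephone option make clear, and that the calendar's adverse event row has been read correctly as ending at that contact. It does not support a claim that safety collection stops on Day 27, that deaths are missed, or that the MTD is at risk. It is a low-priority correction, worth making because it costs almost nothing.

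**What to change.** Reconcile the two passages by changing the tolerance in Study Calendar footnote 3 from plus-or-minus 3 days to + 3 days, as in Section 5.6. Because footnote 3 would then state its own window, the calendar's general two-sided rule would no longer apply to this contact.

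Add an instruction that the contact asks about events through Day 30 after the last dose, whichever of Days 30-33 it takes place on. Every patient reached is then asked about the full SAE window.

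The cost is one symbol and one sentence in the protocol, and 3 days less scheduling flexibility for sites, for a contact that may be made by phone. No analysis, sample size or dose-escalation rule changes.

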11. MEASUREMENT OF EFFECT

Although response is not the primary endpoint of the phase I portion of this trial, patients with measurable disease will be assessed by standard criteria. For the purposes of this study, patients should be re-evaluated every 8 weeks (with a window of minus 1 week prior to day 1 of the cycle). In addition to a baseline scan, confirmatory scans will also be obtained at least 4 weeks following initial documentation of an objective response. Every attempt should be made to use a consistent imaging modality for each individual participant.

11.1 Antitumor Effect – Solid Tumors

For the purposes of this study, patients should be re-evaluated for response every 8 weeks (with a window of minus 1 week prior to day 1 of the cycle).

Response and progression will be evaluated in this study using the new international criteria proposed by the revised Response Evaluation Criteria in Solid Tumors (RECIST) guideline (version 1.1) [*Eur J Ca* 45:228-247, 2009]. Changes in the largest diameter (unidimensional measurement) of the tumor lesions and the shortest diameter in the case of malignant lymph nodes are used in the RECIST criteria.

11.1.1 Definitions

Evaluable for toxicity. All patients will be evaluable for toxicity from the time of their first treatment with trametinib, dabrafenib, and INCB039110.

Evaluable for objective response. Only those patients who have measurable disease present at baseline, have received at least one cycle of therapy, and have had their disease re-evaluated will be considered evaluable for response. These patients will have their response classified according to the definitions stated below. (Note: Patients who exhibit objective disease progression prior to the end of cycle 1 will also be considered evaluable.)

Evaluable Non-Target Disease Response. Patients who have lesions present at baseline that are evaluable but do not meet the definitions of measurable disease, have received at least one cycle of therapy, and have had their disease re-evaluated will be considered evaluable for non-target disease. The response assessment is based on the presence, absence, or unequivocal progression of the lesions.

11.1.2 Disease Parameters

Measurable disease. Measurable lesions are defined as those that can be accurately measured in at least one dimension (longest diameter to be recorded) as ≥ 20 mm by chest x-ray or as ≥ 10 mm

with CT scan, MRI, or calipers by clinical exam. All tumor measurements must be recorded in millimeters (or decimal fractions of centimeters).

Note: Tumor lesions that are situated in a previously irradiated area might or might not be considered measurable. *If the investigator thinks it appropriate to include them, the conditions under which such lesions should be considered must be defined in the protocol.*

Malignant lymph nodes. To be considered pathologically enlarged and measurable, a lymph node must be ≥ 15 mm in short axis when assessed by CT scan (CT scan slice thickness recommended to be no greater than 5 mm). At baseline and in follow-up, only the short axis will be measured and followed.

Non-measurable disease. All other lesions (or sites of disease), including small lesions (longest diameter <10 mm or pathological lymph nodes with ≥ 10 to <15 mm short axis), are considered non-measurable disease. Bone lesions, leptomeningeal disease, ascites, pleural/pericardial effusions, lymphangitis cutis/pulmonitis, inflammatory breast disease, and abdominal masses (not followed by CT or MRI), are considered as non-measurable.

Note: Cystic lesions that meet the criteria for radiographically defined simple cysts should not be considered as malignant lesions (neither measurable nor non-measurable) since they are, by definition, simple cysts.

'Cystic lesions' thought to represent cystic metastases can be considered as measurable lesions, if they meet the definition of measurability described above. However, if non-cystic lesions are present in the same patient, these are preferred for selection as target lesions.

Target lesions. All measurable lesions up to a maximum of 2 lesions per organ and 5 lesions in total, representative of all involved organs, should be identified as **target lesions** and recorded and measured at baseline. Target lesions should be selected on the basis of their size (lesions with the longest diameter), be representative of all involved organs, but in addition should be those that lend themselves to reproducible repeated measurements. It may be the case that, on occasion, the largest lesion does not lend itself to reproducible measurement in which circumstance the next largest lesion which can be measured reproducibly should be selected. A sum of the diameters (longest for non-nodal lesions, short axis for nodal lesions) for all target lesions will be calculated and reported as the baseline sum diameters. If lymph nodes are to be included in the sum, then only the short axis is added into the sum. The baseline sum diameters will be used as reference to further characterize any objective tumor regression in the measurable dimension of the disease.

Non-target lesions. All other lesions (or sites of disease) including any measurable lesions over and above the 5 target lesions should be identified as **non-target lesions** and should also be recorded at baseline. Measurements of these lesions are not required, but the presence, absence, or in rare cases unequivocal progression of each should be noted throughout follow-up.

